10 INFORMED CONSENT PROCESS

The informed consent process will be initiated before a volunteer agrees to participate in the study and will continue throughout the individual's study participation. The participant will sign the informed consent document before any procedures are undertaken for the study. A copy of the signed informed consent document will be given to the participant for his/her records. The consent will explain that participants may withdraw consent at any time throughout the course of the trial. Extensive explanation and discussion of risks and possible benefits of this investigation will be provided to the participants in understandable language. Adequate time will be provided to ensure that the participant has time to consider and discuss participation in the protocol.

The consent form will describe, in detail, the study interventions / procedures and risks / benefits associated with participation in the study. The rights and welfare of the participants will be protected by emphasizing that their access to and the quality of medical care will not be adversely affected if they decline to participate in this study.

10.1 Participant Confidentiality

Participant confidentiality is strictly held in trust by the participating investigator, his staff, and their agents. This confidentiality includes documentation, investigation data, participant's clinical information, and all other information generated during participation in the study.

No information concerning the study or the data generated from the study will be released to any unauthorized third party without prior written approval of the sponsor and the participant.

The study monitor or other authorized representatives of governmental regulatory agencies may inspect all documents and records required to be maintained by the investigator, including but not limited to, medical records (office, clinic, or hospital) and pharmacy records for the participants in this study. The clinical study site will permit access to such records.

10.2 Principal Investigator Responsibility when Participant Withdraws or is Discontinued

If a participant terminates the study early, and is willing, the tests and procedures that would occur at all forthcoming study visits will be completed.

10.3 Future Use of Stored Specimens

Blood samples collected during the study will be sent to and processed by hospital laboratory personnel at University of Minnesota Medical Center, Fairview. Blood will be discarded.

IRB#: 1610M97841

11 PUBLICATION POLICY

The International Committee of Medical Journal Editors (ICMJE) member journals have adopted a trials-registration policy as a condition for publication. This policy requires that all clinical trials be registered in a public trials registry such as ClinicalTrials.gov, which is sponsored by the National Library of Medicine. This protocol will be registered on ClinicalTrials.gov.

27. Wilson KH. Efficiency of various bile salt preparations for stimulation of clostridium difficile spore germination. *J Clin Microbiol*. 1983;18(4):1017-1019.
29. Roediger WE. Decreased sulphur aminoacid intake in ulcerative colitis. *Lancet*. 1998;351(9115):1555.

13 Appendix 1. Schedule of Events

Procedures	Screening	Baseline	Visit 2	Visit 3	Visit 4	Visit 5	Visit 6
		0	Day 7	Day 14	Day 21	Day 28	Day 35
Obtain consent	X						
Medical history	X						
Vitals*	X	X	X	X	X	X	X
Height	X						
Weight	X	X	X	X	X	X	X
Clinical labs ^{1*}		X	X	X	X	X	X
Fasting blood for TMAO and metabolites*		X		X		X	X
Provide stool sample**		X	X	X	X	X	X
24-hour urine collection*		X	X	X		X	X
Diet assignment		X			X		
Dietary History Questionnaire		X					
Provide food diary	X	X	X	X	X	X	X
Review food diary		X	X	X	X	X	X
Adverse events/Concomitant medications		X	X	X	X	X	X

¹Clinical labs include: fasting lipid panel and C-reactive protein (CRP)

*Optional based on PI discretion

**Intermittent stool samples (in frozen collection tubes) will be dropped off at each respective visit following collection. Samples will be collected on days (± 2 days) -4, -2 3, 5, 9, 11, 16, 18, 23, 25, 30, and 32.

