UPIRTSO	Unanticipated Problems Involving Risks to Subjects or Others

PROTOCOL SUMMARY

Title:	Dietary Impact on Intestinal Sulfate Metabolism
Phase:	1
Population:	30 healthy male and female volunteers. Subjects will be recruited from the Twin Cities metropolitan area and will participate as outpatients in this study.
Number of Sites:	1 (University of Minnesota)
Study Duration:	12 months
Subject Participation Duration:	Approximately 1 month
Agent or Intervention:	Dietary intervention will consist of following diets high in sulfur-containing amino acids (SAAs) and low in SAAs for 7 days each, with a 14-day washout period between interventions
Objectives:	The primary objectives of this proposal are to: 1) Compare low sulfur and high sulfur diets with respect to fecal production of hydrogen sulfide (H_2S) and other end products of microbial fermentation; and 2) Determine whether the diet alters the fecal microbiota and the relative proportion of fecal sulfate reducing bacteria.
Endpoints:	The primary endpoint is the change in H_2S concentration measured by gas chromatography. Comparisons will be made between the baseline measurement (Day 0) and end of intervention (Day 7) for each diet (within-group comparison) and between high- and low-sulfur diet H_2S concentration on Day 7 (between group comparison).

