2.4 Exploratory Objectives

1. Assess changes in serum TMAO, carnitine, and phosphatidylcholine concentrations associated with changes in dietary SAA intake.

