2.5.3 Exploratory Outcome Measures

1. Changes in serum concentrations of TMAO, carnitine, and phosphatidylcholine within participants and between High-S vs. Low-S diets.

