4.3 Visit 1 - Baseline (Day 0)

The following procedures are conducted during this visit:

- Measurement of vital signs
- Weight measurement

- Collection of blood samples for clinical labs and research measurements
- Fecal sample collection
- 24-hour urine sample content collection
- Dietitian consult and review of 3-day diet record
- Assignment of first intervention diet, to begin immediately after conclusion of visit
- Receive instructions on completing adverse events diary card
- Review of adverse events and concomitant medications

4.4 Visit 2 (Day 7 ± 2 days; Final day of first diet intervention)

- Vital signs
- Weight
- Collection of blood samples for clinical labs
- Collection of stool sample for research measurements
- Review of 3-day diet record with dietitian
- Review of adverse events and concomitant medications
- 24-hour urine sample content collection
- Urine collection kit provided, to be completed prior to visit 3
- Review of adverse events and concomitant medications

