4.5 Visit 3 (Day 14 ± 2 days)

- Vital signs
- Weight
- Collection of blood samples for clinical labs and research measurements
- Collection of stool sample for research measurements
- 24-hour urine sample content collection
- Review of 3-day diet record with dietitian
- Review of adverse events and concomitant medications

4.6 Visit 4 (Day 21 ± 2 days; First day of second diet intervention)

- Vital signs
- Weight
- Collection of blood samples for clinical labs
- Collection of stool sample for research measurements
- Assignment of second intervention diet, to begin immediately after conclusion of visit
- Review of 3-day diet record with dietitian
- Review of adverse events and concomitant medications
- Urine collection kit provided, to be completed prior to visit 5

4.7 Visit 5 (Day 28 ± 2 days; Final day of second diet intervention)

- Vital signs
- Weight
- Collection of blood samples for clinical labs and research measurements
- Collection of stool sample for research measurements
- 24-hour urine sample content collection

- Review of 3-day diet record with dietitian
- Review of adverse events and concomitant medications

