6 STATISTICAL CONSIDERATIONS

6.1 Sample Size Considerations

This feasibility study plans to enroll 17 participants who will be assigned to receive two dietary interventions in a random order. We anticipate that 2 subjects may drop out from the study for various reasons, including inability to comply with the study visit schedule or new medical

IRB#: 1610M97841

problems unrelated to the study, e.g., use of antibiotics for an infection. The intention of this study is to generate data which will inform the sample size necessary for a larger trial, so power calculations have not been performed.

We will compare primary, secondary, and exploratory outcome measures within each intervention (Day 0 vs. Day 7) and between the two interventions (High-S vs. Low-S) using paired *t*-tests.

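### Research serum is not scheduled at the end of diet 1 (Day 7) or the start of diet 2 (Day 21), so the paired serum tests in Section 6.1 cannot be run as written

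*Combined protocol and SAP*

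**What the plan says.** The exploratory objective in Section 2.4 is "Assess changes in serum TMAO, carnitine, and phosphatidylcholine concentrations associated with changes in dietary SAA intake". Section 2.5.3 makes the outcome "Changes in serum concentrations of TMAO, carnitine, and phosphatidylcholine within participants and between High-S vs. Low-S diets".

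The only analysis statement is in Section 6.1: "We will compare primary, secondary, and exploratory outcome measures within each intervention (Day 0 vs. Day 7) and between the two interventions", by paired t-test. The Protocol Summary, writing of the primary endpoint, shows how the day labels are meant: "between the baseline measurement (Day 0) and end of intervention (Day 7) for each diet (within-group comparison". They count from the start of each diet period.

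The visit headings place the diet boundaries. Diet 1 starts at Visit 1 (Day 0) and ends at "4.4 Visit 2 (Day 7 ± 2 days; Final day of first diet intervention". Diet 2 starts at "4.6 Visit 4 (Day 21 ± 2 days; First day of second diet intervention" and ends at Visit 5 (Day 28).

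In Appendix 1 the row "Fasting blood for TMAO and metabolites" is marked at Baseline and at Visits 3, 5 and 6, and is blank at Visits 2 and 4. The visit lists give "Collection of blood samples for clinical labs and research measurements" at Visits 1, 3, 5 and 6. At Visits 2 and 4 they list blood for clinical labs only. Section 3.4.3 allows blood at all six visits at the PI's discretion and describes the gel-barrier tube for TMAO, but does not say at which visits that tube is drawn.

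**The concern.** A paired test needs both members of the pair from the same person. Without a Day 7 sample, the serum change on the first diet cannot be computed for anyone, and neither can the within-person comparison of the two diets. Without a Day 21 sample, the second diet has no baseline of its own.

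What remains is the change to Day 28 on whichever diet came second, measured from Day 0 (before diet 1) or from Day 14 (mid-washout, nominally 7 days before diet 2 starts). Each diet's serum change then rests on roughly half the participants. A change from Day 0 also spans the whole of diet 1 and the washout, so it takes in any carryover and four weeks of drift. The High-S versus Low-S comparison would be made between people, which gives up the main advantage of the crossover for these outcomes.

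Section 6.1 says the study is meant to inform the size of a larger trial. Serum collected on this schedule cannot supply the within-person, between-diet variance that such a calculation would use.

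**Working it through.** **Step 1: which pairs are scheduled.** Serum days from Appendix 1: 0, 14, 28, 35.

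| Contrast in Section 6.1 | Study days needed | Scheduled for serum? |
|---|---|---|
| Change on diet 1 | 0 and 7 | No (7 missing) |
| Change on diet 2 | 21 and 28 | No (21 missing) |
| High-S vs Low-S, end of diet | 7 and 28 | No (7 missing) |

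None of the three pairs is scheduled. The pairs that do exist, (0, 28) and (14, 28), cover one diet per participant. With serum added at Visits 2 and 4, all three planned pairs are present.

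**Step 2: is this a table-reading fault?** No. The visit lists are a separate source and show the same pattern. The vitals, weight, clinical-lab and stool rows of the same table are filled at Visits 2 and 4.

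**Step 3: can Day 14 stand in?** No. With the ±2-day windows, Visit 3 falls on Days 12 to 16, Visit 2 on Days 5 to 9 and Visit 4 on Days 19 to 23. The windows do not overlap.

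**Step 4: size of the loss.** The plan gives no power figure to reproduce. The documents give N as 15 (Section 3), 17 enrolled with 2 expected dropouts (Section 6.1) and 30 (Protocol Summary). My assumptions are:
- equal correlation ρ between any two measurements on a person;
- every participant gives the optional blood;
- near-equal sequence splits (7/8, 8/9, 15/15);
- two-sided 5% and 80% power, from the noncentral t.

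The unit is the SD of a single measurement across participants.

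Standard errors:
- Paired, all participants: √(2(1−ρ)/N), with N−1 df.
- Within-diet change, only the n who had that diet second: √(2(1−ρ)/n), with n−1 df.
- Day 28 between sequences, adjusted for Day 0: √((1−ρ²)(1/n₁+1/n₂)(1+1/(N−4))), with N−3 df. The last factor allows for estimating the slope.

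For N=15 and ρ=0.5, the paired SE is √(2×0.5/15) = 0.258. The adjusted between-sequence SE is √(0.75×(1/7+1/8)×(1+1/11)) = 0.468.

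Detectable differences at ρ=0.5:

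| N | Within diet: all vs second-diet half | Between diets: paired vs between sequences |
|---|---|---|
| 15 | 0.78 vs 1.16 (n=8) or 1.27 (n=7) | 0.78 vs 1.43 |
| 17 | 0.72 vs 1.07 (n=9) or 1.16 (n=8) | 0.72 vs 1.32 |
| 30 | 0.53 vs 0.78 (n=15) | 0.53 vs 0.94 |

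At N=30 the between-diet figures are 0.63 vs 1.03 at ρ=0.3 and 0.41 vs 0.77 at ρ=0.7. A simulation of the adjusted test at ρ=0.5 gave power of 80.1%, 80.4% and 80.2% at 1.43, 1.32 and 0.94.

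The variance of the between-sequence comparison relative to the paired one is 2/(1−ρ) without adjustment: 2.9, 4.0 and 6.7 at ρ = 0.3, 0.5 and 0.7. With Day 0 adjustment it is 2(1+ρ)(1+1/(N−4)): 2.7, 3.1 and 3.5 at N=30, and 2.8, 3.3 and 3.7 at N=15.

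**The case against.** The strongest counter-argument is Section 3.4.3. It provides for blood at all six visits and then describes both tubes without limiting either, so it could be read as covering research serum on Days 7 and 21. That reading is possible, and serum could be taken on those days. But the section assigns the TMAO tube to no visit, clinical labs alone account for the Visit 2 and 4 draws, and two visit-specific schedules omit it. The texts need reconciling on either reading.

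A second argument is that Day 0 may be the single study baseline, which would make (0, 28) the planned pair for diet 2. That would restore one pair of three. Day 7 would still be missing, so the diet 1 change and the paired between-diet test would still fail.

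Some points limit the finding:
- The documents give no allocation ratio or blocking. Under simple randomisation (assumed), a split of 10/5 or worse has about a 30% chance at N=15, and with n=5 the within-diet figure at ρ=0.5 is 1.68. The half-sample figures are therefore not a worst case.
- The planned before/after test within a diet is itself exposed to time effects. The missing tubes lengthen the interval but do not create that weakness.
- The outcome is exploratory, no power was claimed, and blood is largely at the PI's discretion. Section 4.1 excepts Screening and the Safety Follow-up Visit, whereas Appendix 1 marks the Visit 6 draw optional. That discrepancy touches none of the three pairs.

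**Conclusion.** The concern holds. If the schedule is followed, none of the three serum pairs that Section 6.1 implies can be formed. This result needs no assumption beyond reading the Section 6.1 days as days within each diet. Even with Day 0 as the only baseline, the first-diet change and the paired High-S versus Low-S test cannot be computed. Optional sampling does not rescue the plan, because full compliance with Appendix 1 still gives no Day 7 or Day 21 serum.

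The loss of precision depends on the assumed correlation and near-equal splits. For correlations of 0.3 to 0.7, the between-diet variance is about 2.7 to 3.7 times the paired value after Day 0 adjustment, and 2.9 to 6.7 times without it. The between-sequence comparison also assumes that no diet 1 effect persists to Day 28.

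The matter should be corrected, but its reach is limited to the exploratory serum outcomes.

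**What to change.** Preferred: schedule the missing samples.
- In Appendix 1, mark TMAO blood at Visits 2 and 4.
- In Sections 4.4 and 4.6, list blood for research measurements as well as clinical labs.
- In Section 3.4.3, name the visits at which the gel-barrier tube is drawn.
- While draws stay optional, state that the Day 0, 7, 21 and 28 serum tubes are taken as a set in any participant who has serum drawn. If each draw were made independently with probability 0.7, 0.8 or 0.9 (assumed), only 24%, 41% or 66% of participants would have all four (p⁴), against 70%, 80% or 90% as a set. This narrows the PI's discretion. The two schedule corrections stand without it.

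Alternative, if no serum is added: Section 6.1 should say that serum is analysed as the change to Day 28 on the second diet, compared between sequences with adjustment for Day 0, and that the paired between-diet test does not apply.

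Cost of the preferred route: an amendment to Appendix 1 and Sections 3.4.3, 4.4 and 4.6, and up to two extra serum assay sets per participant. No visit is added and the Visit 3 tube can stay, although it serves no Section 6.1 contrast. Blood for a fasting lipid panel is already listed at Visits 2 and 4. Because it is optional, the change adds a draw wherever those labs would have been skipped.
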